## 15.8. Medtronic Representative Role

Medtronic representatives may participate in the conduct of the study to the extent listed below.

Medtronic representatives can provide technical support to the investigator and other health care personnel as needed during study visits. This support may include the training of site personnel on use of the Medtronic equipment or the protocol-related procedures and forms.

In addition, Medtronic personnel can perform certain activities to ensure study quality. These activities may include:

- Observing testing or medical procedures to provide information relevant to protocol completion
- Reviewing collected data and study documentation for completeness and accuracy
- Perform device programming or device interrogation under the direction of the investigator(s)

Medtronic personnel will not:

- Practice medicine
- Provide medical diagnosis or treatment to subjects
- Discuss a subject's condition or treatment with a subject without the approval and presence of the health care provider.
- Complete CRFs or make entries in the subject's medical record

## 15.9. Direct Access to Source Data/Documents

Source data is all information, original records (or certified copies) of clinical findings, observations or other activities in a study necessary for the reconstruction and evaluation of the study. Examples of these original documents and records include, but are not limited to: hospital/clinic records, phone records, laboratory reports, etc. Site personnel should clearly indicate the subjects' participate in the study within the medical records.

Principal Investigator and Institution must permit study-related monitoring, audits, IRB/EC review and regulatory inspections(s) by providing direct access to source data/documents. Medtronic or third-party auditors representing Medtronic may perform clinical site audits to verify the performance of the monitoring process and study conduct, and to ensure compliance with applicable regulations. Representatives for regulatory bodies such as the FDA or Health Canada may also perform site inspections related to this clinical study. The Principal Investigator, site personnel, and institution will provide auditors with direct access to primary source data and all study-related documentation.

In accordance with GCP and regulatory requirements, Medtronic will investigate suspected cases of fraud.

## 15.10. Confidentiality

Subject confidentiality is assured through the use of subject identification numbers, and the de-identifying of photocopied or records obtained by the Sponsor. In addition to the review of records on site, release of de-identified records to Medtronic may be necessary, such as in the evaluation of adverse events.

For purposes of monitoring this study, access to clinic and hospital records must be available to Medtronic, agents of Medtronic (e.g. CRO), the FDA, Health Canada and other regulatory agencies.

Health Insurance Portability and Accountability Act (HIPAA) language will be required to be included at every site in the US. HIPAA language may be included within the US ICF template.

## 15.11. Liability

### 15.11.1. Study Funding

The costs associated with study conduct will be documented in separate Clinical Trial Agreements that will be signed by Medtronic, the Principal Investigator, and/or the management of the institution.

Subject compensation (if applicable) is detailed in the Patient Informed Consent Form.

### 15.11.2. Insurance

Medtronic of Canada, Ltd., Medtronic International Trading SARL, and Medtronic Logistics LLC are wholly owned subsidiaries of Medtronic, which as the parent company of such entities maintains appropriate clinical study liability insurance coverage as required under applicable laws and regulations and will comply with applicable law and custom concerning specific insurance coverage. If required, a Clinical Trial Insurance statement/certificate will be provided to the EC, governing regulatory authority (if applicable) and/or the IRB.

### 15.11.3. Warranty

Warranty information is provided in the product packaging for commercially available products.

### 15.11.4. Indemnification

Indemnification language will be contained in the Clinical Trial Agreements.

## 15.12. CIP Amendments

Protocol amendments may be initiated by Medtronic to address changes to the conduct of the study. Protocol amendments must be approved by Medtronic and submitted to the IRB/EC and governing regulatory authority (if applicable); protocol amendment approval and approval of any associated changes to the informed consent document must be obtained prior to implementation of the amendment except:

- When necessary to eliminate an immediate/or apparent immediate hazard to participating subjects
- When the change involves purely administrative or logistical aspects of the study

## 15.13. Record Retention

At a minimum, the investigator is responsible for the preparation, review, and retention of the records listed below:

- Essential correspondence that pertains to the investigation
- Records of each subject's case history and exposure to the device. Case histories include the CRFs and supporting data (source documentation), such as:
  - Signed and dated ICFs
  - Medical records, including, for example, progress notes of the physicians, the subject's hospital chart(s) and the nurses' notes
  - All reportable adverse event information
  - Data related to the BE lead, foramen needle, BE kit and therapy evaluation period.
- Documentation of any deviation to the protocol, including the date and the rationale for such deviation
- Signed Investigator Agreement and curriculum vitae for all Investigators
- The protocol and any amendments

The Principal Investigator is responsible for ensuring that all essential study documentation is retained and accessible for a minimum of 2 years following completion of the study. The retention period may be longer if required by Medtronic or local or global regulatory requirements; Medtronic will be responsible for notifying sites of extensions to the 2-year minimum record retention requirements. The Principal Investigator will ensure that essential study documents are not destroyed until written permission has been obtained from Medtronic. Medtronic will be notified in writing of any transfer of study documentation. Medtronic will retain the study records according to Medtronic policy.

## 15.14. Publication and Use of Information

Medtronic intends to publish the results from the study in a timely manner upon study completion. These publication activities may include abstracts, presentations/posters to scientific meetings, and manuscripts.

- [REDACTED]
- [REDACTED]
- [REDACTED]
- [REDACTED]

[REDACTED]

[REDACTED]

### **15.15. Suspension or Early Termination**

Medtronic reserves the right to suspend or terminate the study at any time. Reasons may include, but are not limited to, the following:

- Insufficient enrollment to complete the study within the expected timeframe
- Identification of unacceptable safety profile; suspicion of an unacceptable risk will result in a suspension, confirmation of an unacceptable risk will result in termination
- Product performance/product supply issues

Medtronic reserves the right to suspend or terminate the study at an individual site. Reasons may include, but are not limited to, the following:

- Noncompliance with the protocol
- Serious or repeated deviations at the site
- Failure to implement required corrective and preventive actions
- Insufficient enrollment to complete the study within the expected timeframe
- Loss of appropriately trained site personnel

Investigators are required to notify the IRB/EC and governing regulatory authority (if applicable) of study suspension/termination. Subjects will be notified by the investigator of suspension/termination due to unacceptable risk or of termination due to any other cause.

# Basic Evaluation Lead Post-Market Clinical Follow-up (PMCF) Clinical Investigation Plan

MDT19002

Version 1.0

Page 49 of 49

[Redacted text block]

[Redacted text block]

[Redacted]	[Redacted]	[Redacted]
[Redacted]	[Redacted]	[Redacted]
[Redacted]	[Redacted]	[Redacted]

2. List of Abbreviations and Definitions of Terms

| Abbreviation | Definition |
|--------------|--|
| AE | Adverse Event |
| BASIC | Basic Evaluation Lead Post-Market Clinical Follow-up |
| BE | Basic Evaluation |
| BMI | Body Mass Index |
| CI | Confidence Interval |
| CIP | Clinical Investigational Plan |
| DD | Device Deficiency |
| FAS | Full Analysis Set |
| MedDRA | Medical Dictionary for Regulatory Activities |
| [REDACTED] | [REDACTED] |
| SAP | Statistical Analysis Plan |

3. Introduction

This statistical analysis plan (SAP) is based on Version 1.0 of the Basic Evaluation Lead Post-Market Clinical Follow-up (BASIC) Study. The SAP presents the details of the methods to be used to analyze and report the study results of the BASIC study, protocol number MDT19002.

4. Study Objectives

4.1 Primary Objective

To characterize the proportion of subjects who demonstrate motor or sensory response(s) during lead placement using the InterStim Basic Evaluation (BE) Lead.

[REDACTED]

[REDACTED]

[REDACTED]

[REDACTED]

[REDACTED]

4.3 Safety Assessment

To characterize safety during the BE lead implant and therapy evaluation.

Safety will be evaluated by the collection of reportable adverse events (AEs). Any AE meeting the definition of: serious, device related, therapy related and/or procedure related will be considered reportable for this study.

Device deficiencies (DDs) will be collected and reported.

5. Investigation Plan

This is a single-arm, prospective, multicenter, post market clinical follow-up study to characterize the clinical performance and safety of the InterStim BE lead with the commercially-approved foramen needle and BE kit. The study is intended to be conducted at approximately 30 centers in Europe, Canada, and the United States.

Subjects will complete a baseline visit, BE lead placement visit, and 1-week follow-up visit. Enrollment will be defined as subjects who qualify for all eligibility requirements and undergo the BE lead implant procedure.

The total study duration for a subject is approximately three weeks, depending on when the BE lead implant procedure is scheduled. If a CIP amendment impacts the integrity of a study, the data collected before and after the amendment will be analyzed statistically to assess the effect of the amendment on performance, effective or safety analysis. This analysis will be included in the clinical investigation report.

Inclusion Criteria:

1. Subjects 18 years of age or older
2. Candidate for sacral neuromodulation in accordance with the InterStim System labeling
3. Have a diagnosis of OAB as demonstrated by either urinary urge incontinence and/or urinary frequency on a 3-day voiding diary
4. Willing and able to accurately complete study diaries, questionnaire, attend visits, and comply with the study protocol
5. Willing and able to provide signed and dated informed consent

[figure not shown]
Exclusion Criteria:

1. Have neurological conditions such as multiple sclerosis, clinically significant peripheral neuropathy or spinal cord injury (e.g., paraplegia)
2. Have implantable pacemakers, or defibrillators
3. Have primary stress incontinence or mixed incontinence where the stress component overrides the urge component
4. Have knowledge of planned MRIs, diathermy, microwave exposure, high output ultrasonic exposure, or RF energy exposure not included within the scanning conditions provided with the InterStim System labeling
5. Women who are pregnant or planning to become pregnant during participation in the study
6. Characteristics indicating a poor understanding of the study or characteristics that indicate the subject may have poor compliance with the study protocol requirements
7. Concurrent participation in another clinical study that may add additional safety risks and/or confound study results.*

*Subjects in concurrent studies can only be enrolled with permission from Medtronic. Please contact Medtronic's study manager to determine if the subject can be enrolled in both studies.

The following will be conducted:

1. Baseline
2. Enrollment / Basic Evaluation Lead Implant Procedure
3. Therapy Evaluation
4. One Week Follow-up Visit (Study Exit)

6. Determination of Sample Size

Subjects will be enrolled to obtain a sample size of approximately 100 subjects who complete a BE lead placement with motor or sensory threshold testing to confirm clinical performance. The sample size of approximately 100 subjects is driven to obtain precision of the primary endpoint. Assuming that motor or sensory response is able to be obtained in 95% of subjects who qualify for a BE lead placement, with 100 subjects, this produces a two-sided 95% Confidence Interval (CI) of 88.7-98.4% with a width equal to 9.6%. The CI width will vary slightly depending on the actual proportion of subjects with motor or sensory responses.

7. Statistical Methods

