# Basic Evaluation Lead Post-Market Clinical Follow-up (PMCF) Clinical Investigation Plan

MDT19002

Version 1.0

Page 8 of 49

Medtronic

	
defined as subjects who qualify for all eligibility requirements and undergo the basic evaluation lead implant procedure.
 
The total study duration for a subject is approximately three weeks, depending on when the basic evaluation lead implant procedure is scheduled.

Sample Size	
Subjects will be enrolled to obtain a sample size of approximately 100 subjects who complete a basic evaluation with motor or sensory threshold testing to confirm clinical performance. The sample size of approximately 100 subjects is driven to obtain precision of the primary endpoint.
 
Assuming that motor or sensory response is able to be obtained in 95% of subjects during the basic evaluation lead placement, with 100 subjects, this produces a two-sided 95% Confidence Interval (CI) of 88.7-98.4% with a width equal to 9.6%. The confidence interval width will vary slightly depending on the actual proportion of subjects with motor or sensory responses.

Inclusion/Exclusion Criteria	
Inclusion Criteria:
 

1. Subjects 18 years of age or older

2. Candidate for sacral neuromodulation in accordance with the InterStim System labeling

3. Have a diagnosis of OAB as demonstrated by either urinary urge incontinence and/or urinary frequency on a 3-day voiding diary

4. Willing and able to accurately complete study diaries, questionnaire, attend visits, and comply with the study protocol

5. Willing and able to provide signed and dated informed consent

 
Exclusion Criteria:
 

1. Have neurological conditions such as multiple sclerosis, clinically significant peripheral neuropathy or spinal cord injury (e.g., paraplegia)

2. Have implantable pacemakers, or defibrillators

3. Have primary stress incontinence or mixed incontinence where the stress component overrides the urge component

4. Have knowledge of planned MRIs, diathermy, microwave exposure, high output ultrasonic exposure, or RF energy

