#### **13.1.1. Sample Size Justification**

[REDACTED]

Using PASS 2011, assuming that motor or sensory response is able to be obtained in 95% of subjects who qualify for a BE lead placement, with 100 subjects, this produces a two-sided 95% CI of 88.7-98.4% with a width equal to 9.6%. The confidence interval width will vary slightly depending on the actual proportion of subjects with motor or sensory responses.

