7.2 General Methodology

There is no hypothesis testing in this study.

Continuous measures will be reported as N, means, medians, standard deviations, minimums and maximums. Categorical measures will be reported in frequency distributions including counts and percentages.

For outcomes examining change from baseline, change (Δ) will be calculated as follow-up scores (S_v) minus baseline scores (S_0).

$$\Delta = S_v - S_0$$

Percent change will be calculated as 100 times the change divided by the baseline score.

$$\text{Percent change} = 100 * \Delta / S_0$$

Data analysis will be performed by Medtronic-employed statisticians or designees. A validated statistical software package will be used for the analyses of the study results (e.g. SAS version 9.4 or higher).

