7.9.1.3 Analysis Methods and Presentation Format

Subjects who had the BE lead placement and provide data will be included in the primary analysis. The primary analysis will report the proportion of subjects who obtain motor or sensory response and its two-sided exact binomial 95% CI among those who had lead placement. This will be done separately for leads and the needles used to place the leads.

In cases where surgical modifications for BE leads are needed, motor or sensory response from the initial lead placement will be used for the primary analysis.

In cases where subject's motor or sensory response is not tested, or response data are lost during lead placement, or other reasons where missing data occur, a sensitivity analysis will be performed by displaying the full range of proportions on the potential impact of missing data by running an analysis assuming all missing values as not obtaining a response (worst case) to all missing values as obtaining motor or sensory response (best case).

In addition to the subject level analysis described above, a lead and needle level supporting analysis will be performed by estimating the proportion of BE Leads and needles that had motor or sensory response(s) during initial lead placement. The leads and needles that had motor or sensory responses during replacement BE lead implant will be summarized separately.

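### Does the sample size justification mislead by saying that the confidence interval width varies only slightly with the observed response proportion?

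*SAP*

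**What the plan says.** SAP section 6 sets the target: "Subjects will be enrolled to obtain a sample size of approximately 100 subjects who complete a BE lead placement with motor or sensory threshold testing". The reason given is precision; the Protocol synopsis puts it in the same words: "The sample size of approximately 100 subjects is driven to obtain precision of the primary endpoint".

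One scenario supports the number. It begins "Assuming that motor or sensory response is able to be obtained in 95% of subjects who qualify for a BE lead placement", and for 100 subjects it continues "this produces a two-sided 95% Confidence Interval (CI) of 88.7-98.4% with a width equal to 9.6" (percent). The next sentence in SAP section 6 is "The CI width will vary slightly depending on the actual proportion of subjects with motor or sensory responses". Protocol section 13.1.1 has the same sentence with the abbreviation written out, "The confidence interval width will vary slightly depending on the actual proportion of subjects with motor or sensory responses", and the synopsis repeats it.

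The analysis matches the planning method. SAP section 7.9.1.3 states: "The primary analysis will report the proportion of subjects who obtain motor or sensory response and its two-sided exact binomial 95% CI". SAP section 7.2 states: "There is no hypothesis testing in this study". The visible text gives no success threshold, no maximum acceptable width, and no widths at other proportions. In Protocol section 13.1.1, a redacted block stands directly before the calculation.

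**The concern.** With no hypothesis to power, precision carries the argument for 100 subjects, so a statement about how stable that precision is deserves a check. Near the upper end of the scale, the width of an exact binomial interval changes quickly with the observed proportion. It shrinks towards 100% and grows as the proportion falls. A reader who takes *slightly* at face value would expect roughly 9.6 points, with a lower limit about 6 points under the estimate, over any plausible result. At 90 responders of 100, the interval is 12.7 points wide and its lower limit is 82.4%, which is 7.6 points under the estimate.

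This could matter because Protocol section 6.2 foresees that the performance data may support claims for the product, and Protocol section 6 ties the 100 subjects to confirming clinical performance. Someone judging in advance whether 100 is enough might rely on a precision that holds only near the assumed 95%.

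**Working it through.** **Inputs.** n = 100, assumed proportion 95%, two-sided 95% confidence (SAP section 6, Protocol section 13.1.1); exact binomial interval (SAP section 7.9.1.3).

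**Formula.** For x responders of n, the Clopper-Pearson limits are

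- lower = 0.025 quantile of Beta(x, n − x + 1)
- upper = 0.975 quantile of Beta(x + 1, n − x), or 1 if x = n.

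**Step 1: the plan's own figure.** With x = 95, Beta(95, 6) gives 88.72% and Beta(96, 5) gives 98.36%. The width is 9.64 points, so the stated 88.7-98.4% and 9.6 reproduce. Other methods at 95/100 do not: the widths are Wald 8.54, Wilson 9.02 and Jeffreys 8.68. Agresti-Coull gives 9.59, but with limits 88.54-98.13%. The planning calculation therefore used the same exact method as the analysis.

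**Step 2: other results with 100 subjects.**

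| Responders | Exact 95% CI (%) | Width (points) | Difference from 9.64 | Ratio to 9.64 |
|---|---|---|---|---|
| 85 | 76.5-91.4 | 14.89 | +5.25 | 1.54 |
| 90 | 82.4-95.1 | 12.72 | +3.08 | 1.32 |
| 93 | 86.1-97.1 | 11.03 | +1.39 | 1.14 |
| 94 | 87.4-97.8 | 10.37 | +0.73 | 1.08 |
| 95 | 88.7-98.4 | 9.64 | 0 | 1.00 |
| 96 | 90.1-98.9 | 8.83 | −0.81 | 0.92 |
| 97 | 91.5-99.4 | 7.89 | −1.75 | 0.82 |
| 99 | 94.6-99.97 | 5.42 | −4.22 | 0.56 |
| 100 | 96.4-100 | 3.62 | −6.02 | 0.38 |

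**Step 3: how likely these results are if the true proportion is 95%.** With X ~ Binomial(100, 0.95):

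- The 2.5% and 97.5% points of X are 90 and 99. Over that range the width runs from 12.72 down to 5.42, a factor of 12.72 / 5.42 = 2.3.
- P(94 ≤ X ≤ 96) = 0.51, where the width stays within 1 point of 9.64.
- P(93 ≤ X ≤ 97) = 0.75, where it stays within 1.8 points.
- P(X ≤ 90) = 0.028, P(X ≥ 99) = 0.037, and P(X ≤ 85) is about 0.0001.
- The expected width is 9.42 points, slightly narrower than the planned 9.64.

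**Step 4: what uses the sentence.** SAP section 7.2 rules out hypothesis testing, and SAP section 7.8 plans no interim analysis. The result that SAP section 7.9.1.3 calls for is the observed proportion with its exact interval, computed from the data. Nothing in that computation takes the planned 9.6 points as input.

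**The case for a change.** The case for an edit is this. The sentence is a quantitative statement, and by the plan's own method it is too mild. A spread from 5.4 to 12.7 points arises by chance alone when the 95% assumption is exactly right. The chance that the width differs from 9.64 by 10% or more is 1 − 0.51 = 0.49. To hold about 9.6 points at an observed 90% would take about 170 subjects (153/170 gives 9.59). The sentence appears three times beside the only visible sample size rationale, and a short table would put it right.

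All of that arithmetic stands, and *slightly* is a poor word. The consequence does not follow, for four reasons.

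- Readers are not promised 9.6 points whatever happens. All three places condition the figure on 95% and say that the width moves with the result. Only the size of the movement is understated.
- The departures that could hurt are the wide intervals. At a true 95%, a width of 12.7 points or more has a probability of 2.8%. Results above 95 responders give better precision than planned.
- No claim or lower bound is specified that a limit of 82.4% would fail. The 170-subject figure would matter only if the plan required a width of 9.6 points at 90%, and it does not.
- It cannot be said that 95% is unsupported or that precision at 95% is the whole rationale, because of the redacted block in Protocol section 13.1.1.

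A table of widths would inform a reader, but anyone who wants it can derive it from n and the named method.

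**Conclusion.** The stated interval and width are right. The one inaccuracy is an adverb that plays down a range of about 5.4 to 12.7 points over 99 to 90 responders of 100. No change to the plan is needed, because there is nothing to gain: the sample size stays at about 100, the exact interval is reported in any case, and the primary result is the same under either wording. An analyst following the SAP as written reaches a sound estimate with an honest statement of its uncertainty.

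This rests on two conditions. First, the study remains descriptive, with no performance threshold or required width; none appears in the visible text. Second, the primary denominator is close to 100, as the enrolment target intends. The probabilities quoted also take the plan's 95% as the true proportion. If the true proportion were lower, wider intervals would be more common, and the reported interval would show it. If the protocol is amended for another reason, dropping the adverb or giving the range would be a courtesy to the reader.
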